7.3 General Subject Population

The Sponsor expects to implant up to 20 subjects in this clinical feasibility study across 12 study sites in the United States. Prior to recruitment, written approval of the investigational plan and informed consent form will be obtained from the FDA and associated participating study center Institutional Review Boards (IRB). Study participants are required to meet the study inclusion criteria (provided below) as determined by the respective, referring medical/hearing care providers. All consented participants meeting the study inclusion criteria and not meeting any of the exclusion criteria will be implanted with the commercially available HiResolution Bionic Ear Cochlear Implant System (HiRes 90K™ Advantage implant with the HiFocus™ 1J electrode, HiRes 90K™ Advantage implant with the HiFocus™ Mid-Scala electrode or the HiRes™ Ultra Implant with the HiFocus™ Mid-Scala electrode and currently commercially available AB sound processor (i.e. Naída family external sound processor). A participant's ability to undergo the surgical procedure for cochlear implantation is determined respectively by the participant's managing medical/hearing care providers at his/her implant center.

7.4 Inclusion and Exclusion Criteria

General Inclusion criteria:

- Ability to provide Informed Consent
- 18 years of age or older
- English language proficiency (to be confirmed via case history as having graduated 8th grade level)
- Willingness to participate in all scheduled procedures outlined in the protocol
- Willingness to use an approved cochlear implant signal processing strategy in an everyday listening program during study

Audiometric Inclusion criteria:

Ear to be Implanted:

- Severe-to-profound sensorineural hearing loss (>70 dB HL) as defined by the pure tone average for 500, 1000, 2000 and 4000 Hz
- CNC word recognition score up to ≤30% (tested in subject's everyday listening condition for that ear)
- Duration of severe-to-profound sensorineural hearing loss (>70 dB HL) >3 months and ≤10 years in the ear to be implanted only

Contralateral (non-implanted) ear:

- Up to a moderate sensorineural hearing loss (<70 dB HL) as defined by the pure tone average for 500, 1000, 2000 and 4000 Hz
- CNC word recognition score >30% (tested in subject's everyday listening condition for that ear)

Exclusion Criteria:

- Previous experience with a cochlear implant
- Cochlear malformation or obstruction (i.e. ossification) that would preclude full insertion of electrode array in the *ear to be implanted*
- Medical or psychological conditions that contraindicate surgery or impact the ability to manage an implanted device or the study related procedures as determined by the investigator
- Diagnosis of auditory neuropathy/dys-synchrony in either the ear to be implanted or the contralateral ear
- Active middle-ear disease/infection in the ear to be implanted
- Unrealistic expectations regarding potential benefits, risks and limitations inherent to implant surgical procedures as determined by the investigator
- Unwillingness or inability of subject to comply with all investigational requirements as determined by the investigator

7.5 Participant Withdrawal

Study participants may withdraw from the study at any time, with or without reason, and without prejudice to further treatment. The study site investigator(s) and/or study Sponsor has the right to discontinue study participants. Participants can be discontinued for the following reasons:

- Voluntary withdrawal of consent made by the participant
- A safety concern identified by the Principal Investigator, the Sponsor, or any third party
- Inability of the subject to perform the tasks necessary to provide usable data for the study
- Failure to attend a follow-up visit after three documented attempts to contact the subject and reschedule the visit

Participants who withdraw or who are discontinued from the study will be reported accordingly to the Institutional Review Board. If a subject was discontinued because of a device-related adverse event or serious adverse event (SAE), the subject must be followed until the serious adverse event is resolved, the point at which the subject withdraws HIPAA authorization, or the study is concluded.

The Investigator (or authorized delegate) in cooperation with the study monitor will complete a tracking log and/or enter into the electronic data capturing system the disposition of each enrolled subject (completed study, withdrew, discontinued).

8.0 Study Procedures

8.1 Recruitment

Participants who meet the study criteria will be recruited from adult hearing-impaired patient populations at the participating study centers. A participant's willingness and ability to meet the follow-up requirements will be determined and informed consent will be obtained. A signed and dated informed consent will be kept in the participant's study record and copy provided to the participant. Study participants must also sign a release that authorizes access of medical records to the study sponsor, investigators, monitors and the FDA prior to proceeding with screening assessments. This release may be its own signature line contained within the Informed Consent Form (see Appendix B for template) or may be a separate authorization, consistent with institutional policy.

8.2 Participant Screening

No investigational procedures are used to screen patients for study eligibility. Subjects eligible to participate in this study will be evaluated according to the inclusion requirements for the study. Informed consent will be obtained before any study-specific tests or procedures are conducted. An individual is considered to be enrolled as a study participant only after the informed consent document has been signed and dated. Each subject will be assigned a unique identifier at the time of enrollment.

8.3 Test Metrics or Procedures

The monosyllabic CNC word test will be used as the primary test metric for preimplant candidacy determination and follow-up postimplant performance assessments in the treated ear. The AzBio Sentence test in noise will be used as the primary test metric to assess the binaural hearing condition (implanted + non-implanted ear) performance pre-to-postoperatively.

Given the asymmetrical clinical population for which this feasibility study is being conducted, standard audiometric clinical masking procedures during audiometric and speech perception metrics will be applied as needed to reduce any potential contribution of the better hearing ear during these assessments.

In order to isolate the ear to be implanted and/or treated ear during certain test conditions (i.e. aided testing), a foam earplug and an over-the-head earmuff will be used in the contralateral (non-implanted ear). This method will be referred to in the remainder of this document as 'plug and muff.'

8.3.1 Audiometric Measures:

Standard audiometric practice and procedures are applied for the testing of inter-octave frequencies if necessary.

[figure not shown]
- Unaided air conduction thresholds using insert earphones at octave frequencies will be obtained for each ear at 250, 500, 1000, 2000, 4000 and 8000 Hz. Clinical masking used as appropriate.
- Unaided bone conduction hearing thresholds for each ear at 500, 1000, 2000 and 4000 Hz

8.3.2 Speech Perception Measures:

General speech perception testing procedures

All speech perception testing will be conducted using recorded stimuli presented from a single loudspeaker in at a minimum a single-walled sound booth capable of accommodating a calibrated, 90 degree speaker orientation. Audiometers will conform to ANSI standards for pure-tone and speech audiometry and/or Manufacturer Specifications.

Speech perception measures conducted in soundfield are to be administered via a loudspeaker at 0° azimuth at a distance of one meter from the subject. Speech signals will be presented at 60 dB A. Speech levels will be calibrated to 60 dB SPL using a microphone placed at the approximate position of the subject's head (one meter from loudspeaker).

IMPORTANT NOTE REGARDING POSTOPERATIVE TESTING: Audiometric and speech perception testing at post device activation intervals is to be conducted prior to any device re-programming and/or adjustment of MAP parameters. It is recommended that a listening check of the participant's device and confirmation of sufficient battery life be verified prior to testing at each study interval.

Consonant-Nucleus-Consonant (CNC) Word Recognition Test

The CNC monosyllabic word test (Peterson and Lehiste, 1962) is a validated test of openset word recognition ability. The test will be administered in quiet at 60 dBA (target 0° azimuth) and scored as total number of words correct which will be expressed for results/reporting as percentage correct. The CNC word test is the primary speech perception metric used for study inclusion determination and postoperative outcome comparison at defined intervals for this feasibility study.

AzBio Sentence Test

The AzBio Sentence Test (Spahr and Dorman, 2005) is a validated test of open-set sentence recognition ability. The test is scored as total number of words correct which is expressed for results/reporting as percentage correct. The sentence test tokens include

both male and female speakers. The AzBio Sentence test will be administered at 60 dBA + 5 dB SNR in noise using Speech-spectrum Noise (SSN) in three conditions:

- Speech Front, Noise Front (Target and noise 0° azimuth)
- Speech Front (0° azimuth), Noise directed to the *ear to be implanted/implanted* ear (90° or 270° azimuth)
- Speech Front (0° azimuth), Noise directed to the non-implanted ear (90° or 270° azimuth)

Lateralization Testing

The AzBio Sentence test will additionally be used as the metric to assess lateralization. The test will be administered in soundfield in quiet at 40 dBA. The participant will be positioned face-forward and centered between the right and left speakers (located at 45°) and at a one meter distance (typical calibrated test position) in the audiometric sound suite. A single list of interleaved sentences varying between right and left speaker presentations will be administered. The participant will be asked to identify if the sentence is heard from the right or left speaker. Scoring is based on number correct that the participant identifies from which speaker the sentence was detected.

8.3.3 Patient Questionnaire(s):

Speech, Spatial and Sound Qualities Questionnaire (SSQ)

The SSQ (Gatehouse and Noble, 2004; Noble and Gatehouse 2006) will be used as a subjective, self-reported assessment of hearing status and hearing capability in everyday life prior to and during the feasibility study. The questionnaire is designed to measure self-reported auditory disability across a wide variety of domains to include: hearing speech in a variety of competing contexts; directional, distance and movement components of spatial hearing; segregation of sounds and attending to simultaneous speech streams; ease of listening; naturalness; clarity and identifiability of different speakers and music. The current standard versions of SSQ (5.6) and SSQ-B (5.6) will be used in the study.

Glasgow Benefit Inventory (GBI)

The GBI (Robinson, Gatehouse and Browning, 1996) is a subjective, postintervention questionnaire developed specifically to evaluate any otorhinolaryngological (ORL) interventions. Patient benefit is the change in health status resulting from the intervention. The GBI will be administered postoperatively.

Tinnitus Handicap Inventory (THI)

The THI (Newman, Jacobson and Spitzer, 1996) will be used as a subjective, self-reported measure to quantify the impact of tinnitus on daily living. The questionnaire will be administered pre and postoperatively only if the participant reports tinnitus.

Additional Metrics:

Sponsor developed patient-report subjective questionnaire/scales such as sound quality and/or quality of life related aspects may additionally be administered at various study intervals during the feasibility study only to obtain further relevant input from patients

with this clinical hearing profile receiving this type of treatment. The study intervals are identified within the study protocol when Sponsor developed subjective assessments are to be used.

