Using AzBio Sentence Test in Quiet - One list presented at 40 dBA in soundfield in the
participant's bilateral, everyday listening condition. The participant is asked to identify if
the sentence was detected from the left or right speaker. The sentence delivery from
right or left speaker is randomized.

Note: Participants may or may not be aided in one or both ears thus, testing may be aided or unaided or a combination during test administration). The test setup is as follows:

• Participant will be centered and faced forward between a right and left speaker (each positioned in corners of the audiometric suite at 45° respectively)

Self-Assessment Questionnaire(s):

- Speech, Spatial and Sound Qualities (SSQ) Questionnaire standard version (Version 5.6)
- Tinnitus Handicap Inventory (THI) Administered only if participant has reported tinnitus
- Sponsor developed patient report questionnaire/scale

Implant Surgery:

Conducted at participant's managing hearing care clinical center. Note: Implant surgery to be completed within 26 weeks of the Baseline Visit. If the surgery date exceeds this time frame, Baseline measures including audiometric and speech perception testing will need to be reevaluated.

Initial Device Activation/Fitting:

Device activation should occur within 3 to 6 weeks postimplant surgery.

Device Programming – Sound Processor Fitting: Specific Instruction:

 Study participants are to be provided with a standard everyday program with the following FDA approved signal processing strategy(ies):

HiRes™ Optima with ClearVoice

Additional programs and parameter settings are deferred to the guidance and recommendations of the participant's managing hearing care specialist.

Audiometric Testing:

- Unaided air-conduction thresholds using insert earphones at 250, 500, 1000, 2000, 4000 and 8000 Hz; unilateral, each ear. Clinical masking as appropriate.
- Unaided bone-conduction hearing thresholds at 500, 1000, 2000 and 4000 Hz;
 unilateral, each ear

Adverse Event Assessment:

An adverse event assessment is completed by the investigator at each test interval. An assessment will be completed additionally if an adverse event has occurred outside of the scheduled study test intervals (i.e. unscheduled visit).

3 and 6 Month Postimplant Test Intervals:

The three and six month post-device activation visits to occur within 12 and 24 weeks respectively (+/- 14 days) of the participant's device activation date.

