11.0 Efficacy Measures

Collection of efficacy data to support product approval is not part of this feasibility study. As such, no formal statistical hypothesis is being posed and/or applied. As part of this feasibility study, the following data will be collected and evaluated:

- Monosyllabic word recognition performance in quiet using the CNC word test pre-to
 post device activation at 12 months will be compared, tabulated and summarized.
 Specifically, the CNC word scores postoperatively will be compared to the pre-implant
 word score for the implanted ear. Individual and group comparisons will be completed.
 The intent is to understand the benefit of the implant treatment option and restoration
 of auditory input results in improved speech understanding.
- 2. Audiometric hearing thresholds at the 12 month postoperative test interval will be compared to preimplant thresholds. Individual and group comparison is confirmatory to assess that hearing acuity in the non-implanted ear (better hearing ear) is not affected significantly by cochlear implant treatment in the opposite ear (poorer hearing ear).
- 3. Sentence recognition scores in noise using the AzBio Sentence Test pre-to-post device activation will be compared, tabulated and summarized. Specifically, the everyday, bilateral listening condition AzBio sentence scores at the 12 month postimplant test interval will be compared to the preimplant bilateral sentence score. Individual and group comparisons will be conducted. The intent of this comparison is to evaluate the contribution and/or benefit of the implant treatment option (provision of binaural sensory input) in an asymmetrical hearing loss population.
- 4. To understand if the restoration of binaural sensory input in a single-sided deafness/asymmetrical hearing loss population results in improved ability in lateralization of sound. Using the AzBio Sentence metric, the month postimplant outcome will be compared to preoperative ability. Individual and group comparisons will be conducted.

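### Lateralization at 40 dBA, with no record of whether each sentence was heard, cannot separate one-sided audibility from restored binaural hearing in participants whose unaided better ear does not hear that level

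*Combined protocol and SAP*

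**What the plan says.** Section 8.3.2 sets the lateralization level: "The test will be administered in soundfield in quiet at 40 dBA". Section 9.0 repeats 40 dBA at baseline and at 3, 6 and 12 months. The speakers stand at 45° to the right and left, one metre away. The material is described as follows: "A single list of interleaved sentences varying between right and left speaker presentations will be administered". The response is: "The participant will be asked to identify if the sentence is heard from the right or left speaker". The scoring is: "Scoring is based on number correct that the participant identifies from which speaker the sentence was detected". Nothing says what to record or score when a sentence is not heard.

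For the better ear, Section 7.4 admits: "Up to a moderate sensorineural hearing loss (<70 dB HL) as defined by the pure tone average". It also requires a CNC word score above 30% in that ear's everyday condition. Section 9.0 gives that test at 60 dBA, through insert earphones if the ear is unaided. The glossary lets the better ear be unaided in everyday use, and the lateralization instructions carry this note at every tested visit: "Participants may or may not be aided in one or both ears thus, testing may be aided or unaided or a combination".

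Section 11.0 item 4 states the purpose: to learn whether restoring binaural input "results in improved ability in lateralization of sound", by comparing the postimplant with the preoperative result. The synopsis names 12 months for this comparison.

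**The concern.** A right/left score measures direction only if the sentences are heard from both speakers. The plan shows that the better ear handles speech at 60 dBA, then tests lateralization 20 dB lower without checking audibility there. A participant whose unaided better ear passes at 60 dBA but hears little at 40 dBA, and whose other ear has a severe-to-profound loss, may hear almost nothing at baseline. After activation the implant may make the implant-side sentences audible. Hearing or not hearing a sentence then indicates the speaker, and one ear is enough for that.

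The interpretation of item 4 is at stake. Section 10.0 plans, at a minimum, to count subjects as improved, unchanged or worse. With up to 15 subjects, a few gains of this kind could change the summary, and they would be read as binaural benefit. The recorded data could not show otherwise, because no heard/not-heard information is collected.

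**Working it through.** The documents give no target, power or expected score for lateralization, so there is no plan figure to reproduce.

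**Inputs from the documents.** Lateralization level 40 dBA; better-ear CNC level 60 dBA; CNC limit above 30%; better-ear pure tone average below 70 dB HL; two speakers; number correct; one list per visit.

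**Assumptions.** Right and left sentences are evenly split. The offset from dBA to dB HL is not given, so 0 to 20 dB is used. List length is not stated, so 10, 20 and 30 sentences are tried.

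**Step 1: which ears are at risk.** Level in dB HL = level in dBA − offset.

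| Assumed offset | 40 dBA is about | 60 dBA is about | Distance from 40 dBA to the 70 dB HL limit |
|---|---|---|---|
| 0 dB | 40 dB HL | 60 dB HL | 70 − 40 = 30 dB |
| 10 dB | 30 dB HL | 50 dB HL | 70 − 30 = 40 dB |
| 20 dB | 20 dB HL | 40 dB HL | 70 − 20 = 50 dB |

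At every offset a 20 dB band of flat losses lies between the two test levels. An unaided ear in the lower part of that band can pass CNC at 60 dBA and hear little or nothing at 40 dBA.

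**Step 2: expected score at baseline with nothing heard.** Every sentence guessed: 50%. Every unheard sentence scored wrong: 0%. If silence is always answered with the same side, half the answers are right: 50%.

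**Step 3: expected score at 12 months with one-sided hearing.** Let all implant-side sentences be heard, and let q be the share heard from the other speaker. A one-ear listener places every heard sentence on the implant side, so heard sentences from the other speaker are wrong.

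- Unheard guessed: 0.5 + 0.5 × (1 − q) × 0.5. At q = 0 this is 75%, at q = 0.5 it is 62.5%, at q = 1 it is 50%.
- Unheard answered as the other side: 0.5 + 0.5 × (1 − q). At q = 0 this is 100%, at q = 0.5 it is 75%, at q = 1 it is 50%.
- Unheard scored wrong: 50% for any q.

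**Step 4: gain with no binaural comparison, at q = 0.**

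| Handling of unheard sentences, same at both visits | Baseline | 12 months | Gain |
|---|---|---|---|
| Guessed | 50% | 75% | 25 points |
| Answered as the other side | 50% | 100% | 50 points |
| Scored wrong | 0% | 50% | 50 points |

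If handling differs between visits or sites, the same hearing gives anything from 50 − 50 = 0 points (guessed, then scored wrong) to 100 − 0 = 100 points (scored wrong, then answered as the other side).

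**Step 5: would it show in one participant?** With 20 sentences, moving from all guessing to one side heard and the rest guessed raises the score with probability 0.95. The smallest score with an upper tail of at most 0.05 under chance is 15 of 20 (exact tail 0.0207). The one-side listener who guesses the rest reaches it with probability 0.62. With 10 sentences (cut 9) the probability is 0.19, and with 30 (cut 20) it is 0.94.

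**The case against.** **The CNC criterion protects much of the range.** A reader might infer from the 70 dB HL limit that unaided better ears up to just under that value are exposed. The documents do not support this. An unaided ear must score above 30% at 60 dBA, which is about 40 to 60 dB HL on the offsets above. A flat loss near 70 dB HL lies above that level and could hardly pass. A steeply sloping loss might pass, but would probably have enough low-frequency hearing to detect speech at 40 dBA. Nor can one loss, such as 50 dB HL, be named as affected: at an offset of 10 dB that ear is at threshold during CNC, and at 20 dB it is below threshold. This objection stands and limits the point to mild-to-moderate unaided loss.

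**The test is not stated to be forced choice.** A reader might infer forced guessing and a 50% baseline. The plan names two answers but does not require one for an unheard sentence, and its scoring wording refers to detection. Unheard could be scored wrong, giving 0%. This also stands, and it makes the missing rule part of the defect.

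**The full one-sided pattern is an assumption.** Nothing in the documents shows that an implant would hear every sentence from one speaker and none from the other. The gain shrinks as q rises when unheard sentences are guessed or answered as the other side. If the implant hears both speakers equally and the better ear hears neither, a chance score is the correct result at 40 dBA, not a missed ability.

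**The stakes are limited.** This is a feasibility study with no formal hypothesis and no efficacy claim for approval, and audible soft speech on the deaf side is arguably a benefit in itself. That is fair, but item 4 asks specifically about binaural input. Unaided thresholds in each ear at baseline and 12 months would allow a rough look at audibility. No such analysis is planned, and thresholds do not show which sentences were heard.

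**Conclusion.** The point holds for participants whose better ear is unaided, passes CNC at 60 dBA and does not reliably hear 40 dBA. For them a pre-to-12-month gain of 25 to 50 points is possible from one-sided audibility alone, under consistent handling of unheard sentences, and item 4 would read it as restored binaural input. These sizes rest on an even split of sentences, nothing heard at baseline, and complete one-sided hearing at 12 months. The band of losses rests on the assumed 0 to 20 dB offset.

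The documents do not say how many of the up to 15 participants fall in this group, and it could be none. Participants who hear 40 dBA well are unaffected. A reader might infer that the lateralization endpoint is invalid as a whole, or that the level must rise to 60 dBA. Neither follows. At a fixed 60 dBA one ear could still use loudness differences between near and far speakers, and results would no longer be comparable with baselines already taken at 40 dBA. What is supported is a low-cost gap in recording and reporting.

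**What to change.** Keep 40 dBA, the right/left answer and the number-correct score at every visit.

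- In Section 8.3.2 and the baseline, 3 and 6 month, and 12 month parts of Section 9.0, add a heard/not-heard mark for each sentence. State one scoring rule for unheard sentences that applies at all sites and visits.
- In Section 11.0 item 4, report each participant's share of sentences heard by speaker side (implant side and other side) beside the lateralization score, at baseline and 12 months. The split by side is necessary: someone who hears one side only would score 100% on heard sentences alone.
- Report separately the participants who do not hear the list from both speakers at baseline, and do not attribute their change to binaural input.

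The cost is one extra mark per sentence and a short table, with no added visit or list. The wording change must go through the formal amendment route in Section 14.4.1. Anyone already tested will have no heard/not-heard data for those visits. The change separates detection from direction; it does not remove one-ear loudness cues among sentences that are heard.
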